i. Patiromer. Patiromer dosing will be determined based on fasting potassium concentrations measured at the end of each week, factoring in both the absolute concentration, as well as the rate of change. The baseline dose of patiromer will correspond to the study by Weir et al. (2015); 8.4-g once per day for participants with a baseline serum potassium of ≥ 5.1 mEq/L. The following dosing schedule (Table 2) will be used for managing hyperkalemia during the study:

Table 2. Dosing of patiromer during the study based on serum potassium concentrations

Potassium	Change in Potassium	Action
<3.8 mEq/L	Same or decreased	Contact study nephrologist to determine dose
<3.8 mEq/L	Increased	Continue with current dose
3.8-5.0 mEq/L	Changed <0.5 mEq/L	Continue with current dose
3.8-5.0 mEq/L	Changed ≥ 0.5 mEq/L	Continue with current dose, but notify study nephrologist
5.1-6.0 mEq/L	Decreased	Continue with current dose
5.1-6.0 mEq/L	Same or increased	Contact study nephrologist to determine dose
>6.0 mEq/L	Decreased	Continue with current dose, but notify study nephrologist
>6.0 mEq/L	Same or increased	Contact study nephrologist to determine dose

ii. Research Diets. The guidelines for research diets are outlined in Table 3. With the exception of the Dairy Food Group, diets will be balanced according to the USDA MyPlate. Diets will be based on a 7-day menu cycle, and will be reviewed by participants during the screening visit. In order to promote participant adherence with the diets, participants will be permitted to select appropriate substitutes based on their food preferences from a list of pre-approved substitutes. For example, if a participant does not like to eat apples, they may substitute this for a list of other low-potassium fruits.

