iii. Serum potassium concentrations. The primary purpose of this study is to evaluate the efficacy of patiromer for maintaining serum potassium concentrations in CKD patients during transition to a liberalized plant-rich diet by comparing fasting serum potassium concentrations at screening to values at the end of phase I (week 2) and phase II (week 4) of the study. However, because potassium concentrations are also being used to titrate the dose of patiromer needed to achieve normal potassium concentrations, fasting serum potassium concentrations will also be measured at the end of weeks 1 and 3. To ensure a rapid response to changes in serum potassium concentrations, blood samples obtained at the CTSI CRC will be immediately delivered to the study laboratory at Tisch Hospital for analysis, and the results sent to the CTSI Pharmacy for evaluation (section 10.a.i.). Participants will be directed to pick up new prescriptions from the CTSI Pharmacy on the days of measurement. To obtain a measurement of serum potassium concentration, a 0.5 mL sample of blood is required.

iv. Blood pressure. Systolic and diastolic blood pressures will be measured after 5-minutes of rest in a seated position with their arm supported at the level of their heart and their feet resting on the floor using an automatic sphygmomanometer. Blood pressure measurements will be obtained in duplicate with a third measure obtained if the systolic or diastolic values on repeated measurement differ by more than 5 mmHg.

v. Gastrointestinal symptoms. The frequency and severity of participant gastrointestinal symptoms in the previous week (abdominal cramping, abdominal discomfort, indigestion, infrequent or difficult to pass bowel movements, flatulence, loose or watery stools) will be self-reported via an investigator-developed questionnaire at baseline, and at the end of the stabilization period (week 1), phase I diet (week 2), and phase II diet (week 4).

vi. Other biochemical parameters. Fasting blood samples will be obtained at the CTSI CRC, and analyzed for concentrations of phosphorus, calcium, magnesium, albumin, glucose, insulin, cholesterol, LDL-cholesterol, HDL-cholesterol, triglycerides, urea nitrogen, bicarbonate and C-reactive protein. Similar to serum potassium concentrations, blood samples will be delivered by study staff to the laboratory at Tisch Hospital for analysis. To obtain these biochemical measurements, approximately 5.0 mL of blood is required.

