Once half of the participants are enrolled and accrued, the PI ([name]) will review serum potassium concentrations to ascertain if there were any episodes of moderate-severe hyperkalemia, or protocol issues that require reporting, withdrawing a participant and/or stopping the study. An AE is any unfavorable and unintended sign, symptom, or disease, including worsening of pre-existing medical conditions. The criteria for withdrawing participants are outlined in section 14 below. The study will be stopped if there is a serious adverse event (SAE) related to the study. Any SAE related to the intervention will be reported to the NYU School of Medicine Institutional Review Board by phone and email within 24-hours of being notified. To minimize participant risk and facilitate monitoring, we plan to enroll cohorts of ≤ 2 participants rather than a single cohort of 10 participants. Summary data and safety monitoring reports will be submitted to the NYU School of Medicine Institutional Review Board during annual review, or if there are changes in the risk/benefit ratio of the study.

As per our Clinical Trial Agreement with Relypsa, Inc., the PI will undergo training in reporting AEs by Relypsa, Inc. before starting the study, and will report all AEs that occur after the signing of informed consent, and up to 14 days after the intervention to the Drug Safety and Pharmacovigilance (DSPV) Department at Relypsa, Inc within 15 days of completing the study. Any AEs that are considered serious (SAEs), which occur will be reported to Relypsa, Inc. DSPV Department within 24-hours of being identified/reported. SAE include “any untoward medical occurrence that at any dose: (i) results in death; (ii) is immediately life threatening (i.e. in the opinion of the investigator, the AE places the subject at immediate risk of death; it does not include a reaction that, had it occurred in a more severe form, might have caused death); (iii) requires inpatient

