Prior to the intervention, participants will receive education on the signs and symptoms of hyperkalemia; muscle weakness, abnormally slow or rapid heart rate, and heart palpitations (from Patient education: Hyperkalemia (the basics); UpToDate.com)⁶. Participants will be directed to monitor themselves for these conditions, and to go to the emergency room if they start experiencing them, making sure to notify the emergency department staff about their participation in the study. Standard treatment for acute episodes of hyperkalemia includes intravenous infusions of calcium gluconate and glucose/insulin, often followed by polystyrene sulfonate or emergent dialysis to remove excess potassium. The emergent treatment of adverse events will be at the discretion of the attending physician. In the event of any admission to the emergency room (even if determined to be unrelated to hyperkalemia), participants will be asked to alert the study PIs as soon as possible.

The intervention contains several features to lower the risk of hyperkalemia. For one, the research diets will be prepared for participants to provide control over the dietary potassium exposure. We will use the feeding study approach that gradually increases dietary potassium in a step-wise manner in order to prevent large shifts in dietary potassium intake. During phase I, participants will be stabilized on a plant-rich diet that restricts dairy products and excludes fruits and vegetables that are high in potassium. This closely approximates the current dietary recommendations for CKD patients with hyperkalemia, but does include plant-based foods from the Protein Foods Group (legumes, nuts, seeds), which are high in potassium (>200 mg/serving). However, compared to the typical Western diet, plant-rich diets are more alkaline, and are higher in fiber, factors that are thought to help control serum potassium concentrations⁴. After a week of consuming this diet, high-potassium fruits and vegetables will be introduced, and make up half of the fruit and vegetable servings. We will closely monitor participants’ adherence to the research diets through daily food records to ascertain their adherence with the study diets – participants that are determined to be non-adherent with the research diets at the end of phase I (defined in section 14) will be withdrawn from the study.

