Another intervention feature to lower the risk of hyperkalemia is the close monitoring of participants’ serum potassium concentrations to adjust the dose of patiomer (10.a.i. Table 2). We will measure serum potassium concentrations as per current patiomer recommendations (weekly), and samples will be processed through the Tisch Laboratory, and the results sent to the CTSI Pharmacy for review. If values are abnormally high or rapidly increasing towards hyperkalemia (10.a.i. Table 2), the study nephrologist ([name]) will be immediately contacted. Because hemolysis can cause artificially elevated serum potassium values, participants with abnormally high or rapidly increasing concentrations of serum potassium will have another blood test to confirm their serum potassium concentrations.

In addition to risks associated with hyperkalemia, there are potential risks related with patiromer use. In a sample of 734 patients treated with patiromer, the most common AEs were constipation (7.2%), hypomagnesemia (5.3%), diarrhea (4.8%), nausea (4.8%), abdominal discomfort (2.0%) and flatulence (2.0%). It is likely that the most common of these AEs (constipation, hypomagnesemia, diarrhea) would be attenuated by a plant-rich diet, which contains higher amounts of fiber and magnesium compared to the typical Western diet. The less common adverse events (abdominal discomfort, flatulence) may be exacerbated by the higher intakes of dietary fiber. These potential AEs will be assessed at the end of each week through the gastrointestinal symptoms questionnaire, and blood testing at the end of phase I and II (for hypomagnesemia). Patiromer also has the potential to bind to other medication, reducing their absorption. This will be mitigated by directing patients to take patiromer once daily, and at least 3 hours away from other medications.

It is unlikely that women and men with stages 3-4 CKD will become pregnant or impregnate someone. Additionally, we will exclude anyone who is planning on becoming pregnant from the study. As part of our Clinical Trial Agreement with Relypsa, Inc., we will report any pregnancies (whether female or male impregnating a female) to Relypsa, Inc. In addition, because the patiromer and the research diets are untested in pregnant women, we will withdraw women who become pregnant during the study period.

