This study will not provide the investigators with data to demonstrate improvements in health-related quality of life, morbidity, mortality, and utilization or cost of care. However, if proven efficacious, future CKD patients may benefit from the knowledge generated from this study regarding the need to limit or avoid high-potassium plant foods, and the potential health benefits of a plant-rich dietary pattern. Because this is a

proof-of-concept study, the emphasis has been placed on safety and internal validity rather than real-world applicability and generalizability to the CKD population. Consequently, this is just a first step in several needed to benefit future CKD patients. Additional longer-term studies in free-living CKD patients would be needed before any such changes in practice could be realized.

16) Vulnerable populations

No vulnerable populations are included in this study.

17) Multi-site research

Not applicable.

18) Community-based participatory research

Not applicable.

19) Sharing results with subjects

The study results will not be shared with participants who will be expected to return to usual care practices upon completion of the study.

20). Setting

Research activities will occur at the CTSI CRC and Renal Clinic of the New York VA. Ethical review will be obtained from the Institutional Review Board at NYULMC.

21) Resources available

i). Personnel.

INVESTIGATORS

[name] (Principal Investigator, Effort = 0.6 CM) is a Professor in the Departments of Medicine and Neuroscience and Physiology at the New York University School of Medicine, and Chief of Nephrology at the Renal Clinic of the New York VA. He is a nephrologist with extensive clinical and research experience with individuals with chronic kidney disease, including trials of medications. He is well-known in the local nephrology community. [name] is co-investigator to [name] ongoing Diabetes Healthy Hearts study (R01), and pending Kidneys and Behavioral Management of Phosphorus study (R21). He will provide crucial medical oversight to the study, in particular safety monitoring, patiomer prescriptions, and assist with interpretation of data from a medical perspective in the dissemination of study results. [name] has a part-time university position and his effort is estimated as a function of his university appointment.

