A brief description of the study will be provided at the time of screening for the study. After reviewing the consent form with patients, and after they have signed the consent form, we will verify that they meet the inclusion/exclusion criteria (sections 5.i and 5.ii.). Potential participants will be shown the research diet menus to determine whether they are willing and able to adhere to the research diets. All questions will be answered.

A copy of the consent form will be given to the participant and they will be encouraged to contact the PIs with any and all questions that occur at any time during the conduct of the study. No patients will be excluded on the basis of race/ethnicity, but this pilot study has a sample size that is insufficient to examine differences in the intervention by race/ethnicity.

30) Process to document consent in writing

Patient's consented participation in this study will be documented in their medical record.

31) Drugs or devices

Participants in this study will be prescribed patiromer (dosing 10.a.i. Table 2), under the supervision of the study nephrologist ([name]). Patiromer is an FDA-approved cation-exchange polymer that binds to potassium in the digestive tract, and is excreted (along with bound potassium) in feces. Patiromer is indicated for the treatment of hyperkalemia, and is demonstrated to result in clinically significant reductions in serum potassium concentrations. The safety concerns associated with patiromer, along with measures to reduce these complications, are noted in section 13, and include constipation (7.2%), hypomagnesemia (5.3%), diarrhea (4.8%), nausea (4.8%), abdominal discomfort (2.0%) and flatulence (2.0%), and binding to other medications.

References.

1. United States Renal Data System. 2016 USRDS annual data report: Epidemiology of kidney disease in the United States. National Institutes of Health, National Institute of Diabetes and Digestive and Kidney Diseases, Bethesda, MD, 2016.
4. St-Jules DE, [name] DS, Sevick MA. Nutrient non-equivalence: Does restricting high-potassium plant foods help to prevent hyperkalemia in hemodialysis patients? *J Ren Nutr* 2016;26(5):282-287.

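### Table 2 asks for no nephrologist contact when potassium is 5.1-6.0 mEq/L and has fallen by any amount, so a participant still mildly hyperkalemic at week 2 can start the phase II diet with only pharmacy review assured

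*Combined protocol and SAP*

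**What the plan says.** Section 9.a (Design) sets a one-week stabilization on usual diet, one week of the low-potassium plant-rich diet (phase I), then the liberalized diet in weeks 3 and 4 (phase II). Section 12 describes the switch in terms of time: "After a week of consuming this diet, high-potassium fruits and vegetables will be introduced, and make up half of the fruit and vegetable servings".

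Section 9.a.i, Table 2, governs dosing from the weekly fasting potassium. The row at issue reads "5.1-6.0 mEq/L Decreased Continue with current dose". No minimum fall is given. Two other rows that also keep the dose unchanged (3.8-5.0 mEq/L with a change of 0.5 or more, and above 6.0 mEq/L and decreased) read "Continue with current dose, but notify study nephrologist".

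Section 9.b.iii says that samples go to the laboratory at once, "and the results sent to the CTSI Pharmacy for evaluation". Section 12 repeats that routing and adds "If values are abnormally high or rapidly increasing towards hyperkalemia (10.a.i. Table 2), the study nephrologist" is contacted immediately. It gives no number for an abnormally high value. I read its cross-reference as the Table 2 now in 9.a.i.

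Section 4 classes 5.1 to <6.5 mEq/L as mild hyperkalemia and withdraws participants at 6.5 or above. Section 12 names hyperkalemia-related cardiotoxicity as the major risk.

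**The concern.** The protocol relies on two protections against its named major risk: raising dietary potassium in steps, and weekly potassium checks that lead to dose adjustment. The week 2 value is where the two should meet, because it is the last one before high-potassium produce is added. The next scheduled potassium is a week later. At that point the protocol has a stated check on dietary adherence (sections 12 and 13), but none on potassium below 6.5.

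Table 2 can pass such a participant without the nephrologist hearing of it. The rule is also uneven. A move from 5.5 to 5.0, which is into the normal range, requires a notification. A move from 5.9 to 5.8, which is still hyperkalemic by the protocol's own definition, does not. At stake is an unremarked decision to leave the dose alone just before dietary potassium rises. The analysis is not at stake.

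**Working it through.** The plan gives no figure to reproduce. The check has two parts: a reading of Table 2 as a decision rule, and an illustration of how that rule behaves.

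**1. The four rows above 5.0 mEq/L (Table 2).**

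| Potassium | Change | Nephrologist involved? |
|---|---|---|
| 5.1-6.0 | Decreased | No |
| 5.1-6.0 | Same or increased | Yes, contacted for dose |
| >6.0 | Decreased | Yes, notified |
| >6.0 | Same or increased | Yes, contacted for dose |

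**2. A path through the table (assumed values).** Screening 6.4, week 1 5.9, week 2 5.8. Both weeks fall in the first row. The participant stays on 8.4 g/day, is below the withdrawal limit, and starts phase II at 5.8 with no Table 2 contact.

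**3. What week 1 already catches.** With values to 0.1 mEq/L, reaching the first row at week 2 needs a week 1 value of at least 5.2. Table 4 schedules potassium at screening and weeks 1-4, not at baseline, so I take the week 1 change from screening. If week 1 was above 6.0, or was 5.2-6.0 and not below screening, Table 2 has already involved the nephrologist. Only two falls in a row, with week 1 at 5.2-6.0, give no trigger at either week.

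**4. Illustration.** The documents give no on-treatment values and no within-person SD, so every input here is an assumption:
- true screening value uniform on 5.3-5.8;
- a true fall by week 1 and none after;
- independent normal error at screening, week 1 and week 2, with SD 0.1 / 0.2 / 0.3;
- values rounded to 0.1;
- recorded screening 5.1-6.4 and week 1 below 6.5;
- 2,000,000 draws per case.

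No trigger = P(row at week 2) x (1 - share of the row flagged at week 1). For example, with no true fall and SD 0.1: 0.364 x (1 - 0.837) = 0.059.

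| True fall | Reach row at week 2 | Of these, flagged at week 1 | No trigger at either week (of all) | No trigger and week 2 at 5.6 or above (of all) |
|---|---|---|---|---|
| 0 | 36 / 41 / 39% | 84 / 76 / 74% | 5.9 / 9.8 / 10.2% | 1.5-1.7% |
| 0.2 | 33 / 34 / 30% | 30 / 50 / 58% | 23.2 / 16.9 / 12.8% | 0.6-0.8% |
| 0.3 | 27 / 27 / 24% | 10 / 36 / 50% | 24.3 / 17.3 / 12.2% | 0.5% or less |
| 0.5 | 13 / 12 / 12% | 0 / 16 / 35% | 12.6 / 10.3 / 7.9% | 0.5% or less |

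At a true fall of 0.8 the no-trigger share is 0.1-1.6%, and at 1.0 about 0-0.2%. With a screening range of 5.1-5.5 instead, it is 5-7% for no fall, 4-7% for a fall of 0.3 and 0.1-1.4% for a fall of 0.5.

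**5. How high the untriggered values are.** With no true fall, 5.6 or above makes up about a quarter of the untriggered cases at SD 0.1 (1.5/5.9) and about a sixth at SD 0.2-0.3 (1.7/9.8). With a true fall of 0.2 it is 3-6% (0.6/23.2 to 0.8/12.8). Most untriggered values are therefore just above normal.

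**6. In people.** 10 x 6% to 10 x 24% is 0.6 to 2.4 participants with no trigger. At 5.6 or above it is at most 10 x 1.7% = 0.17.

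**The case against.** **The value is reviewed.** A reader might infer from Table 2 that nobody has to look at it. The documents do not support that: sections 9.b.iii and 12 send every weekly result to the CTSI Pharmacy for evaluation. What is missing is required nephrologist review.

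**The nephrologist prescribes.** Section 9.a has the study nephrologist prescribe patiromer, and 9.b.iii has participants collect new prescriptions on measurement days. This may mean a prescriber's decision at every visit, or a new prescription only when the dose changes. The text does not settle which, so it softens the gap without closing it.

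**Other oversight exists.** Section 21 says of the principal investigator: "He will provide crucial medical oversight to the study, in particular safety monitoring, patiomer prescriptions". Section 31 places patiromer "under the supervision of the study nephrologist". Both are general. Section 12's contact for abnormally high values has no cut-off and points back to Table 2. Its scheduled review, in which the investigator "will review serum potassium concentrations to ascertain if there were any episodes of moderate-severe hyperkalemia" or reportable protocol issues, falls once, at half enrolment.

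**The row is deliberate.** Section 9.a.i bases dosing on both level and rate of change, and holding the dose while potassium falls on treatment is reasonable. The participant is within the range enrolled, treated, below the previous value, taught the symptoms, retested in a week and withdrawn at 6.5. This stands. The point does not dispute the dose, only the lack of a notice at the diet step.

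**The numbers could mislead.** A reader might take 5.9 to 5.8 as typical, or 6-24% as the share entering phase II at such levels. Under the same assumptions at most 1.7% are at 5.6 or above. This stands too.

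**Conclusion.** The point holds in a limited form. Table 2 requires no nephrologist contact or notification for 5.1-6.0 mEq/L after any fall, and no potassium criterion below 6.5 governs the start of phase II. At week 2, only pharmacy review of such a value is assured.

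It is a minor safety gap. A reader might infer that it weakens the trial's result. It does not, because neither the endpoint nor the analysis depends on it. Nor do the documents show that entry at 5.1-6.0 is unsafe, so they give no basis for demanding a potassium bar.

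That Table 2 omits the notice is plain from the text. Frequency is not known. The 6-24% rests wholly on the assumed screening range, true fall of 0 to 0.5 and SD of 0.1-0.3, and drops below 2% if potassium truly falls by 0.8 or more. The change is worth making because it costs almost nothing and concerns the protocol's own named major risk.

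**What to change.** Add to sections 9.a and 12, and as a note to Table 2:

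> *For any week 2 potassium >5.0 mEq/L, including a decreased value, the study nephrologist is notified and records a dose decision before phase II meals start. Below the 6.5 mEq/L withdrawal limit, no fixed potassium level bars entry to phase II.*

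Same or increased values already require contact, so for them this adds only the record and its timing. A simpler option is to change the action for 5.1-6.0 and decreased to "Continue with current dose, but notify study nephrologist" at all weeks, which reuses Table 2's own wording. On its own it sets no timing relative to phase II meals.

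Cost: at most 10 extra notifications at week 2 (10 x 1), or 40 overall if the cell is changed for every week (10 participants x 4 checks). No extra staff or procedure is needed. Phase II meals may wait briefly if the decision is late. If the nephrologist chooses to defer phase II, the week 4 measurement moves with it, so the actual day should be recorded and reported.
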